## 9. STUDY CALENDAR

Baseline evaluations are to be conducted within 1 week prior to administration of protocol therapy. Scans and x-rays must be done 2 weeks prior to the start of therapy. In the event that the patient's condition is deteriorating, laboratory evaluations should be repeated within 48 hours prior to initiation of the next cycle of therapy.

|   | Pre-Study
(D-21 to D-1) | Wk 1   | Wk 2           | Wk 3 | Wk 4           | Wk 5           | Wk 6 | Wk 7           | Wk 8 | Wk 9           | Wk 10-12 | Wk 13          | Off Study      |
|---|----------------------------|--|----------------|------|----------------|----------------|------|----------------|------|----------------|----------|----------------|----------------|
| Vorinostat a                       |                            | X  | X              | X    | X              | X              | X    | X              | X    | X              | X        | X              |                |
| Informed consent                              | X b             |  |                |      |                |                |      |                |      |                |          |                |                |
| Demographics                                  | X b             |  |                |      |                |                |      |                |      |                |          |                |                |
| Medical history n                  | X b,c           |  | X e |      | X e | X e |      | X e |      | X e |          | X e | X              |
| Concurrent meds n                  | X b,c           |  | X e |      | X e | X e |      | X e |      | X e |          | X e | X              |
| Physical exam n                    | X b,c           |  | X e |      | X e | X e |      | X e |      | X e |          | X e | X              |
| Vital signs n                      | X b,c           |  | X e |      | X e | X e |      | X e |      | X e |          | X e | X              |
| Height  | X b             |  |                |      |                |                |      |                |      |                |          |                |                |
| Weight n                           | X b,c           |  | X e |      | X e | X e |      | X e |      | X e |          | X e | X              |
| Performance status (ECOG) n        | X b,c           |  | X e |      | X e | X e |      | X e |      | X e |          | X e | X              |
| Hematology labs d,o                | X c             |  | X e |      | X e | X e |      | X e |      | X e |          | X e | X              |
| Serum chemistry f,o                | X c             |  | X e |      | X e | X e |      | X e |      | X e |          | X e | X              |
| EKG   | X b             |  |                |      |                |                |      |                |      |                |          |                |                |
| Urinalysis                                    | X c             |  |                |      |                |                |      |                |      |                |          |                |                |
| B-HCG g                            | X c             |  |                |      |                |                |      |                |      |                |          |                |                |
| Adverse events evaluation n        |                            |  | X e |      | X e | X e |      | X e |      | X e |          | X e | X              |
| Tumor measurements p               | X c             | Tumor measurements are repeated every 8 weeks ( $\pm$ 1 week) for the first 6 cycles. After 6 months on study, can be performed every 12 weeks ( $\pm$ 1 week). Documentation (radiologic) must be provided for patients removed from study for progressive disease. Objective responses should be confirmed within 4 weeks. |                |      |                |                |      |                |      |                |          |                | X h |
| Archival tumor tissue collected               | X b             |  |                |      |                |                |      |                |      |                |          |                |                |
| Blood for correlative studies j, m |                            | X  |                |      | X              |                |      |                |      |                |          |                |                |

|   |                |  |  |  |                |  |  |  |                |  |  |  |  |  |
|---|----------------|--|--|--|----------------|--|--|--|----------------|--|--|--|--|--|
| PET/CT L   | X c |  |  |  | X i |  |  |  | X i |  |  |  |  |  |
| 
a- Vorinostat: continuous oral dose 400mg/day (or other dosage if drug reduction required).
 
b- Days -21 to day -1: informed consent, physical examination and medical history; vital signs including weight and height; review of concurrent medication; ECG; collection of archival tumor tissue.
 
c- Days -14 to day -1: limited physical examination with vital signs (including weight); review of new events on history; review of medication; performance status; tumor measurement (by CT or MRI) and PET/CT (optional). Laboratory tests, pregnancy test (if appropriate) and urinalysis should be done within 7 days from first drug intake.
 
d- CBC with differential and platelets; PTT, PT and INR.
 
e- Study visits assessments to be done on weeks 2 and 4 (<math>\pm 1</math> day) for the first cycle, then for the second cycle on week 5 and 7, (<math>\pm 1</math> day); then from week 9 on, every four weeks (<math>\pm 1</math> day) thereafter.
 
f- Albumin, alkaline phosphatase, total bilirubin, bicarbonate, BUN, calcium, chloride, creatinine, glucose, LDH, phosphorus, potassium, total protein, AST, ALT, sodium, magnesium.
 
g- Serum pregnancy test (women of childbearing potential).
 
h- Off-study evaluation.
 
i- PET/CT to be done on days -14 to -1; D28<math>\pm 3</math> days and D56<math>\pm 3</math> days (optional).
 
j- Blood for correlative studies on days 1 (prior to first dose of vorinostat), 7 (+-1day) and 28 (+-1day)
 
k- A tumor biopsy will be done if the tumor can be easily accessed.
 
L – PET/CT scans are optional and will be performed based on the availability of funding
 
m- If no blood exists from a selected patient, or the blood was of poor quality, Karmanos study personnel will recontact the patient to obtain new informed consent and draw a new blood sample.
 
n- For patients that have been on study longer than 2 years, office visits can be done every 12 weeks (<math>\pm 7</math> days), with medical history, concurrent meds, physical exam, vital signs, weight, performance status, and adverse events evaluation done also at that time
 
o- For patients that have been on study longer than 2 years, hematology labs and serum chemistry can be done every 6 weeks (<math>\pm 7</math> days)
 
p- For patients that have been on study longer than 2 years, tumor measurements can be done every 24 weeks (<math>\pm 10</math> days)
 |                |  |  |  |                |  |  |  |                |  |  |  |  |  |

## 10. MEASUREMENT OF EFFECT

For the purposes of this study, patients should be re-evaluated for response every 8\_ weeks. Patients may receive scans every 3 cycles/12 weeks ( $\pm$  1 week) after completing 6 months of treatment on study. Patients that have been on study longer than 2 years can have tumor measurements (CT scans or MRI) done every 24 weeks ( $\pm$ 10 days). In addition to a baseline scan, confirmatory scans should also be obtained 4 (not less than 4) weeks following initial documentation of objective response.

### 10.1 Definitions

Response and progression will be evaluated in this study using the new international criteria proposed by the revised Response Evaluation Criteria in Solid Tumors (RECIST) guideline (version 1.1) (58). Changes in the largest diameter (unidimensional measurement) of the tumor lesions and the shortest diameter in the case of malignant lymph nodes are used in the RECIST criteria.

#### 10.1.1 Definitions

Evaluable for toxicity. All patients will be evaluable for toxicity from the time of their first treatment with vorinostat.

Evaluable for objective response. Only those patients who have measurable disease present at baseline, have received at least one cycle of therapy, and have had their disease re-evaluated will be considered evaluable for response. These patients will have their response classified according to the definitions stated below. (Note: Patients who exhibit objective disease progression prior to the end of cycle 1 will also be considered evaluable.)

Evaluable Non-Target Disease Response. Patients who have lesions present at baseline that are evaluable but do not meet the definitions of measurable disease, have received at least one cycle of therapy, and have had their disease re-evaluated will be considered evaluable for non-target disease. The response assessment is based on the presence, absence, or unequivocal progression of the lesions.

#### 10.1.2 Disease Parameters

Measurable disease. Measurable lesions are defined as those that can be accurately measured in at least one dimension (longest diameter to be recorded) as  $\geq$ 20 mm by chest x-ray, as  $\geq$ 10 mm with CT scan, or  $\geq$ 10 mm with calipers by clinical exam. All tumor measurements must be recorded in millimeters (or decimal fractions of centimeters).

Note: Tumor lesions that are situated in a previously irradiated area might or might not be considered measurable.

Malignant lymph nodes. To be considered pathologically enlarged and measurable, a lymph node must be  $\geq$ 15 mm in short axis when assessed by CT

scan (CT scan slice thickness recommended to be no greater than 5 mm). At baseline and in follow-up, only the short axis will be measured and followed.

Non-measurable disease. All other lesions (or sites of disease), including small lesions (longest diameter <10 mm or pathological lymph nodes with  $\geq 10$  to <15 mm short axis), are considered non-measurable disease. Bone lesions, leptomeningeal disease, ascites, pleural/pericardial effusions, lymphangitis cutis/pulmonitis, inflammatory breast disease, and abdominal masses (not followed by CT or MRI), are considered as non-measurable.

Note: Cystic lesions that meet the criteria for radiographically defined simple cysts should not be considered as malignant lesions (neither measurable nor non-measurable) since they are, by definition, simple cysts.

‘Cystic lesions’ thought to represent cystic metastases can be considered as measurable lesions, if they meet the definition of measurability described above. However, if non-cystic lesions are present in the same patient, these are preferred for selection as target lesions.

Target lesions. All measurable lesions up to a maximum of 2 lesions per organ and 5 lesions in total, representative of all involved organs, should be identified as **target lesions** and recorded and measured at baseline. Target lesions should be selected on the basis of their size (lesions with the longest diameter), be representative of all involved organs, but in addition should be those that lend themselves to reproducible repeated measurements. It may be the case that, on occasion, the largest lesion does not lend itself to reproducible measurement in which circumstance the next largest lesion which can be measured reproducibly should be selected. A sum of the diameters (longest for non-nodal lesions, short axis for nodal lesions) for all target lesions will be calculated and reported as the baseline sum diameters. If lymph nodes are to be included in the sum, then only the short axis is added into the sum. The baseline sum diameters will be used as reference to further characterize any objective tumor regression in the measurable dimension of the disease.

Non-target lesions. All other lesions (or sites of disease) including any measurable lesions over and above the 5 target lesions should be identified as **non-target lesions** and should also be recorded at baseline. Measurements of these lesions are not required, but the presence, absence, or in rare cases unequivocal progression of each should be noted throughout follow-up.

### 10.1.3 Methods for Evaluation of Measurable Disease

All measurements should be taken and recorded in metric notation using a ruler or calipers. All baseline evaluations should be performed as closely as possible to the beginning of treatment and never more than 4 weeks before the beginning of the treatment.

The same method of assessment and the same technique should be used to characterize each identified and reported lesion at baseline and during follow-up. Imaging-based evaluation is preferred to evaluation by clinical examination unless the lesion(s) being followed cannot be imaged but are assessable by clinical exam.

Clinical lesions Clinical lesions will only be considered measurable when they are superficial (e.g., skin nodules and palpable lymph nodes) and  $\geq 10$  mm diameter as assessed using calipers (e.g., skin nodules). In the case of skin lesions, documentation by color photography, including a ruler to estimate the size of the lesion, is recommended.

Chest x-ray Lesions on chest x-ray are acceptable as measurable lesions when they are clearly defined and surrounded by aerated lung. However, CT is preferable.

Conventional CT and MRI This guideline has defined measurability of lesions on CT scan based on the assumption that CT slice thickness is 5 mm or less. If CT scans have slice thickness greater than 5 mm, the minimum size for a measurable lesion should be twice the slice thickness. MRI is also acceptable in certain situations (e.g. for body scans).

Use of MRI remains a complex issue. MRI has excellent contrast, spatial, and temporal resolution; however, there are many image acquisition variables involved in MRI, which greatly impact image quality, lesion conspicuity, and measurement. Furthermore, the availability of MRI is variable globally. As with CT, if an MRI is performed, the technical specifications of the scanning sequences used should be optimized for the evaluation of the type and site of disease. Furthermore, as with CT, the modality used at follow-up should be the same as was used at baseline and the lesions should be measured/assessed on the same pulse sequence. It is beyond the scope of the RECIST guidelines to prescribe specific MRI pulse sequence parameters for all scanners, body parts, and diseases. Ideally, the same type of scanner should be used and the image acquisition protocol should be followed as closely as possible to prior scans. Body scans should be performed with breath-hold scanning techniques, if possible.

PET-CT At present, the low dose or attenuation correction CT portion of a combined PET-CT is not always of optimal diagnostic CT quality for use with RECIST measurements. However, if the site can document that the CT performed as part of a PET-CT is of identical diagnostic quality to a diagnostic CT (with IV and oral contrast), then the CT portion of the PET-CT can be used for RECIST measurements and can be used interchangeably with conventional CT in accurately measuring cancer lesions over time. Note, however, that the

PET portion of the CT introduces additional data which may bias an investigator if it is not routinely or serially performed.

Ultrasound Ultrasound is not useful in assessment of lesion size and should not be used as a method of measurement. Ultrasound examinations cannot be reproduced in their entirety for independent review at a later date and, because they are operator dependent, it cannot be guaranteed that the same technique and measurements will be taken from one assessment to the next. If new lesions are identified by ultrasound in the course of the study, confirmation by CT or MRI is advised. If there is concern about radiation exposure at CT, MRI may be used instead of CT in selected instances.

Endoscopy, Laparoscopy The utilization of these techniques for objective tumor evaluation is not advised. However, such techniques may be useful to confirm complete pathological response when biopsies are obtained or to determine relapse in trials where recurrence following complete response (CR) or surgical resection is an endpoint.

Tumor markers Tumor markers alone cannot be used to assess response. If markers are initially above the upper normal limit, they must normalize for a patient to be considered in complete clinical response. Specific guidelines for both CA-125 response (in recurrent ovarian cancer) and PSA response (in recurrent prostate cancer) have been published [*JNCI* 96:487-488, 2004; *J Clin Oncol* 17, 3461-3467, 1999; *J Clin Oncol* 26:1148-1159, 2008]. In addition, the Gynecologic Cancer Intergroup has developed CA-125 progression criteria which are to be integrated with objective tumor assessment for use in first-line trials in ovarian cancer [*JNCI* 92:1534-1535, 2000].

Cytology, Histology These techniques can be used to differentiate between partial responses (PR) and complete responses (CR) in rare cases (e.g., residual lesions in tumor types, such as germ cell tumors, where known residual benign tumors can remain).

The cytological confirmation of the neoplastic origin of any effusion that appears or worsens during treatment when the measurable tumor has met criteria for response or stable disease is mandatory to differentiate between response or stable disease (an effusion may be a side effect of the treatment) and progressive disease.

FDG-PET While FDG-PET response assessments need additional study, it is sometimes reasonable to incorporate the use of FDG-PET scanning to complement CT scanning in assessment of progression (particularly possible 'new' disease). New lesions on the basis of FDG-PET imaging can be identified according to the following algorithm:

- a. Negative FDG-PET at baseline, with a positive FDG-PET at follow-up is a

- sign of PD based on a new lesion.
- b. No FDG-PET at baseline and a positive FDG-PET at follow-up: If the positive FDG-PET at follow-up corresponds to a new site of disease confirmed by CT, this is PD. If the positive FDG-PET at follow-up is not confirmed as a new site of disease on CT, additional follow-up CT scans are needed to determine if there is truly progression occurring at that site (if so, the date of PD will be the date of the initial abnormal FDG-PET scan). If the positive FDG-PET at follow-up corresponds to a pre-existing site of disease on CT that is not progressing on the basis of the anatomic images, this is not PD.
  - c. FDG-PET may be used to upgrade a response to a CR in a manner similar to a biopsy in cases where a residual radiographic abnormality is thought to represent fibrosis or scarring. The use of FDG-PET in this circumstance should be prospectively described in the protocol and supported by disease-specific medical literature for the indication. However, it must be acknowledged that both approaches may lead to false positive CR due to limitations of FDG-PET and biopsy resolution/sensitivity.

Note: A 'positive' FDG-PET scan lesion means one which is FDG avid with an uptake greater than twice that of the surrounding tissue on the attenuation corrected image.

#### 10.1.4 Response Criteria

##### 10.1.4.1 Evaluation of Target Lesions

|                                  |   |
|----------------------------------|---|
| Complete Response (CR):   | Disappearance of all target lesions. Any pathological lymph nodes (whether target or non-target) must have reduction in short axis to <10 mm.   |
| Partial Response (PR):    | At least a 30% decrease in the sum of the diameters of target lesions, taking as reference the baseline sum diameters   |
| Progressive Disease (PD): | At least a 20% increase in the sum of the diameters of target lesions, taking as reference the smallest sum on study (this includes the baseline sum if that is the smallest on study). In addition to the relative increase of 20%, the sum must also demonstrate an absolute increase of at least 5 mm. (Note: the appearance of one or more new lesions is also considered |

progressions).

Stable Disease (SD): Neither sufficient shrinkage to qualify for PR nor sufficient increase to qualify for PD, taking as reference the smallest sum diameters while on study

#### 10.1.4.2 **Evaluation of Non-Target Lesions**

Complete Response (CR): Disappearance of all non-target lesions and normalization of tumor marker level. All lymph nodes must be non-pathological in size (<10 mm short axis)

Note: If tumor markers are initially above the upper normal limit, they must normalize for a patient to be considered in complete clinical response.

Non-CR/Non-PD: Persistence of one or more non-target lesion(s) and/or maintenance of tumor marker level above the normal limits

Progressive Disease (PD): Appearance of one or more new lesions and/or unequivocal progression of existing non-target lesions. Unequivocal progression should not normally trump target lesion status. It must be representative of overall disease status change, not a single lesion increase.

Although a clear progression of “non-target” lesions only is exceptional, the opinion of the treating physician should prevail in such circumstances, and the progression status should be confirmed at a later time by the review panel (or Principal Investigator).

#### 10.1.4.3 **Evaluation of Best Overall Response**

The best overall response is the best response recorded from the start of the treatment until disease progression/recurrence (taking as reference for progressive disease the smallest measurements recorded since the treatment started). The patient's best response assignment will depend on the achievement of both measurement and confirmation criteria.

**For Patients with Measurable Disease (i.e., Target Disease)**

| Target Lesions  | Non-Target Lesions          | New Lesions | Overall Response | Best Overall Response when Confirmation is Required* |
|---|-----------------------------|-------------|------------------|--|
| CR  | CR                          | No          | CR               | ≥4 wks. Confirmation**                               |
| CR  | Non-CR/Non-PD               | No          | PR               | ≥4 wks. Confirmation**                               |
| CR  | Not evaluated               | No          | PR               |  |
| PR  | Non-CR/Non-PD/not evaluated | No          | PR               |  |
| SD  | Non-CR/Non-PD/not evaluated | No          | SD               | documented at least once ≥4 wks. from baseline**     |
| PD  | Any                         | Yes or No   | PD               | no prior SD, PR or CR                                |
| Any   | PD***                       | Yes or No   | PD               |  |
| Any   | Any                         | Yes         | PD               |  |
| * See RECIST 1.1 manuscript for further details on what is evidence of a new lesion.  |                             |             |                  |  |
| ** Only for non-randomized trials with response as primary endpoint.  |                             |             |                  |  |
| *** In exceptional circumstances, unequivocal progression in non-target lesions may be accepted as disease progression.   |                             |             |                  |  |
| Note: Patients with a global deterioration of health status requiring discontinuation of treatment without objective evidence of disease progression at that time should be reported as “ symptomatic deterioration .” Every effort should be made to document the objective progression even after discontinuation of treatment. |                             |             |                  |  |

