#### **Treatment Period:**

Vorinostat will be administered orally once daily continuously at 400 mg. Each treatment cycle will consist of 4 weeks of daily treatment.

Study visits will be conducted on weeks 2 and 4 ( $\pm 1$  day) for the first cycle, then for the second cycle on week 5 and 7, ( $\pm 1$  day); then from week 9 on, every four weeks ( $\pm 1$  day) thereafter for the remainder of the study. Patient medical histories, physical examinations, laboratory tests, assessments of compliance with study medication and recording of adverse events will be conducted during study visits. Further blood may be drawn for research correlatives. For patients that have been on study longer than 2 years, office visits can be done every 12 weeks ( $\pm 7$  days), with medical history, concurrent meds, physical exam, vital signs, weight, performance status, and adverse events evaluation done also at that time. For patients that have been on study longer than 2 years, hematology labs and serum chemistry can be done every 6 weeks ( $\pm 7$  days).

The severity duration and relationship to vorinostat will be determined for each adverse experience (AE) ([Section 11](#)).

Blood will be drawn on days 1 prior to first drug intake, and on days 7 (+- 1 day) and 28 (+- 1 day), prior to drug intake, to assess for correlative studies.

Patients will have radiological tumor assessment by computed tomography (CT) scan (or magnetic resonance imaging - MRI) on days -14 to -1 (prior to the start of vorinostat) and day 56 ( $\pm 3$  days). They will be followed with CT scans or MRI every 2 cycles / 8 weeks ( $\pm 1$  week) thereafter. Patients may receive scans every 3 cycles/12 weeks ( $\pm 1$  week) after completing 6 months of treatment on study. Patients that have been on study longer than 2 years can have tumor measurements (CT scans or MRI) done every 24 weeks ( $\pm 10$  days).

Predicated on obtaining funding, additional scans (optional) will be performed. These will include PET/CT scans prior to treatment, Day 28 ( $\pm 3$  days), and Day 56 ( $\pm 3$  days). An additional CT scan or MRI will also be performed on Day 28 ( $\pm 3$  days) for comparison purposes. The Day 28 CT/MRI and the PET/CT scans will be optional studies- due to financial issues (funding).

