## **2. Tumor Response Evaluation According To RECIST**

### **2.1 Image Acquisition**

Response assessment using RECIST criteria will be performed on all CT scans during the trial. Scans will be performed after administration of oral and IV contrast agents according to institutional practices.

Iodinated intravenous (IV) contrast media may be administered for diagnostic CT scans per standard institutional practice, unless contraindicated. The decision not to use IV contrast for CT is at the discretion of the performing radiologist. If IV contrast is *not* administered for these scans, then these non-contrast CT series can be used for both RECIST and volumetric measurements by prospectively reconstructing the image data into both thick (2.5 to 5 mm) and thin-section (1 to 1.25 mm) series, respectively..

The CT scan with contrast is obtained with arms elevated above the head and at suspended maximal inspiration to provide optimal relative contrast of lung lesions within aerated lung. Typical parameters for image acquisition and reconstruction are shown in Table 2.

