**Confirmation:**

- To be assigned the status of PR or CR, changes in tumor measurements must be confirmed by repeat assessments that should be performed no less than 4 weeks after the criteria for response are first met. Longer intervals as determined by the study protocol may also be appropriate.
- To be assigned the status of SD, follow-up measurements must have met the SD criteria at least once after study entry at a minimum interval (in general, not less than 6-8 weeks) that is defined in the study protocol.

**Duration of Overall Response:** This is measured from the time measurement criteria are met for CR or PR (whichever status is recorded first) until the first date that recurrence or PD is objectively documented, taking as reference for PD the smallest measurements recorded since the treatment started.

**Duration of Stable Disease:** Stable disease is measured from the start of the treatment until the criteria for disease progression are met, taking as reference the smallest measurements recorded since the treatment started. The clinical relevance of the duration of SD varies for different tumor types and grades.

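### Best response of stable disease can rest on one scan at 4 weeks, and the only scheduled scan that early is optional, so SD versus PD can depend on who had it

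*Combined protocol and SAP*

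**What the plan says.** Section 10.1.4.3 defines the endpoint in general terms: "The best overall response is the best response recorded from the start of the treatment until disease progression/recurrence". Its table for measurable disease then gives SD as best response when it is "documented at least once ≥4 wks. from baseline", and PD as best response when there is "no prior SD, PR or CR". The footnote on the SD rule reads "Only for non-randomized trials with response as primary endpoint", which describes this single-arm trial, so the rule applies. The table does not say whether baseline means the date of the baseline scan or day 1 of treatment.

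The Schema (Treatment Period) requires CT or MRI on days -14 to -1 and on day 56 (±3 days), then every 8 weeks. It adds a CT or MRI on day 28 (±3 days), gives comparison as its purpose, and says: "The Day 28 CT/MRI and the PET/CT scans will be optional studies- due to financial issues (funding". Section 10 and the tumor-measurement row of the Section 9 calendar set 8-weekly evaluation and do not mention a day-28 CT/MRI.

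Appendix C, Section 2.1, says: "Response assessment using RECIST criteria will be performed on all CT scans during the trial". Under its Confirmation heading, Appendix C says SD must be met at least once after entry "at a minimum interval (in general, not less than 6-8 weeks) that is defined in the study protocol".

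**The concern.** The SD rule can be met four weeks before the first scan that every patient must have. The only scheduled imaging that can meet it that early is optional. Two patients with the same disease course can therefore receive different best responses because one had a funded extra scan. If uptake of that scan varied by site or by funding period, the SD proportion would vary with it at the same drug effect.

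Three things are at stake:

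- The descriptive SD/PD tabulation. Section 2.1 uses SD rates (50% to 79%) to describe earlier agents in salivary gland tumors and ACC.
- The SD and PD categories in the exploratory VTV correlation (Section 1.3, Appendix I).
- Who enters the exploratory SD-duration analysis (Sections 1.3 and 12.4), if it is limited to patients with best response SD. The plan does not state its population. Patients who progress by day 56 would add durations of about 8 weeks.

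**Working it through.** **1. The plan's own figures.** Section 12.1.1: continue with at least 1 responder of 12, promising with at least 3 of 29, response rates 5% versus 20%.

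- Probability of early termination under the null = 0.95^12 = 0.5404 (stated 0.540).
- P(promising) = sum over x ≥ 1 of Bin(12, x, p) × P(Bin(17, p) ≥ 3 − x). At p = 0.05 this is 0.1480 (limit 0.15); at p = 0.20 it is 0.9005 (stated 0.90).

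The design reproduces. It counts only CR+PR, so moving a patient between SD and PD changes none of these figures.

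**2. The same patient, two classifications.** Take a patient stable at day 28 and progressed at day 56, and suppose the day-28 scan counts.

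| Scans done | Sequence | Best response under the table |
|---|---|---|
| Day 28 and day 56 | SD, PD | SD |
| Day 56 only | PD | PD (no prior SD) |

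**3. Does the day-28 scan meet the 4-week rule?** Let the baseline scan be b days before day 1 (b = 1 to 14, no day 0) and the scan be on day f (25 to 31). The interval is f − 1 + b, and there are 14 × 7 = 98 date pairings.

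- Baseline read as the scan date: the interval runs from 25 − 1 + 1 = 25 to 31 − 1 + 14 = 44 days. At least 28 days requires f + b ≥ 29. This fails for 3 values of b at f = 25, 2 at f = 26 and 1 at f = 27, so 98 − 6 = 92 of 98 pairings qualify.
- Baseline read as day 1: f − 1 ≥ 28 requires f ≥ 29, so 3 of 7 window days qualify.

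**4. Would a later threshold remove the dependence?** In-window day-56 scans fall on days 53 to 59 and in-window day-28 scans on days 25 to 31. With a limit of day 49 from first dose, every day-56 scan qualifies and no day-28 scan does.

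**5. Size.** One patient of 29 is 1/29 = 3.4 points. The documents give no PFS, so take an exponential time to progression with median m as an assumption: S(t) = 0.5^(t/m). The share progressing between weeks 4 and 8 is S(4) − S(8). For m = 3 months (13.04 weeks): 0.8085 − 0.6536 = 0.155, and 0.155 × 29 is about 4.5 patients.

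| Assumed median (months) | Progressing in weeks 4–8 | Patients of 29 |
|---|---|---|
| 3 | 15.5% | 4.49 |
| 6 | 9.1% | 2.63 |
| 9 | 6.4% | 1.85 |
| 12 | 4.9% | 1.42 |

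These figures compare every patient having a qualifying day-28 scan with none having one, so they are upper bounds for each median. If no day-28 scans were done, the effect is nil.

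**The case against.** The strongest reply is that the day-28 scan was never meant to enter best response. The Schema gives comparison as its purpose and places it with the funding-dependent PET work, while Sections 9 and 10 evaluate response every 8 weeks. The case for counting it rests mainly on one sentence in Appendix C. That appendix also differs from Section 10 elsewhere: it allows five target lesions per organ and ten in total, against two and five. This stands in part. Whether the scan counts is unsettled, which is why the point is conditional. But nothing in Section 10.1.4.3 excludes the scan, and a 4-week rule has little use if day 56 is the first assessment that counts.

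A second reply is that no SD rate is a stated objective, and that Section 2.1 of the Background treats SD of 6 months or more as the relevant measure. A patient who progresses by day 56 cannot reach 6 months. This stands and limits the consequence.

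A third is that changing the definition now is post hoc, since Section 8 and Appendix D already report outcomes from this trial. This also stands, and is met by reporting both definitions.

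A reader might also infer stronger points that the documents do not support:

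- That Appendix C contradicts the 4-week rule. Its 6–8 weeks is a general statement that leaves the interval to the protocol, which sets 4 weeks.
- That two weeks of treatment could establish SD. From a day -14 scan, 28 days is reached on day 15, but no scan is scheduled then; the earliest window day is 25.
- That the genomic comparison is distorted. Appendix D contrasts durable benefit with none, and stability ending by day 56 is unlikely to be called durable. Only the looser wording on some benefit in Section 8 leaves room for an effect.

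**Conclusion.** The plan leaves the SD/PD split open to the presence of an optional scan. Conditional on that scan counting, the flip follows directly from the table. It can occur in 92 of 98 date pairings if baseline is the scan date and on 3 of 7 window days if it is day 1.

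The reach is limited to the three descriptive or exploratory uses listed above. CR+PR, alpha, power, early termination and SD over 6 months do not change, and PFS does not change when progression is found on the same day-56 scan. It would be wrong to read this as a threat to the primary conclusion.

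The size is 3.4 points per reclassified patient. The 5 to 16 point range is an all-versus-none upper bound resting on the exponential assumption and medians of 12 to 3 months. The lower end fits better with the indolent disease described in Section 2.1 and with the prolonged SD reported in Section 8 and Appendix D. The documents do not say how many day-28 scans were done, so the actual number affected cannot be derived. The change is worth making because it is cheap and removes an avoidable ambiguity.

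**What to change.** 1. In the Section 10.1.4.3 table, require SD to be documented at or after the first mandatory assessment (the day-56 scan), not earlier than day 49 from first dose. Day 49 is the lower edge of the 8 weeks ±1 week in the Section 9 calendar (56 − 7 = 49). Counting from first dose also settles what baseline means. Align the Confirmation text in Appendix C.
2. State that a day-28 CT/MRI cannot by itself establish SD as best response, and that progression seen on it still counts as PD.
3. State that patients with only a day-28 SD scan and no later assessment go to category 9 (unknown) in Section 12.5.2. They remain non-responders in the main response analysis, as that section already provides for categories 4–9.
4. Because some outcomes are already known, report the SD proportion under both the 4-week and the revised definition, and label the revised one as a later clarification.

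No new scans are needed. The cost is a table cell, a few sentences and one extra tabulation. The reported SD rate may be slightly lower, and a few patients may move from SD to unknown.
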